#### Table 14.3.2.8 Clinical Laboratory Shifts in NCI CTCAE Grades from Baseline to Worst On-Treatment Result Safety Analysis Set

Laboratory Test		•	• •	Wors	t On-Treatmen	t Result	
(Upper or Lower							
Limit of Normal)	Treatment Group	Baseline Result	0	1	2	3	4
Hemoglobin (Low)							
	HP-3070 18.0 mg (N=XX)	0	xx (xx.x)	xx (xx.x)	xx (xx.x)	xx (xx.x)	xx (xx.x)
		1	xx (xx.x)	xx (xx.x)	xx (xx.x)	xx (xx.x)	xx (xx.x)
		2	xx (xx.x)	xx (xx.x)	xx (xx.x)	xx (xx.x)	xx (xx.x)
		3	xx (xx.x)	xx (xx.x)	xx (xx.x)	xx (xx.x)	xx (xx.x)
		4	xx (xx.x)	xx (xx.x)	xx (xx.x)	xx (xx.x)	xx (xx.x)
	HP-3070 9.0 mg (N=XX)	0	xx (xx.x)	xx (xx.x)	xx (xx.x)	xx (xx.x)	xx (xx.x)
		1	xx (xx.x)	xx (xx.x)	xx (xx.x)	xx (xx.x)	xx (xx.x)
		2	xx (xx.x)	xx (xx.x)	xx (xx.x)	xx (xx.x)	xx (xx.x)
		3	xx (xx.x)	xx (xx.x)	xx (xx.x)	xx (xx.x)	xx (xx.x)
		4	xx (xx.x)	xx (xx.x)	xx (xx.x)	xx (xx.x)	xx (xx.x)
	Placebo (N=XX)	0	xx (xx.x)	xx (xx.x)	xx (xx.x)	xx (xx.x)	xx (xx.x)
		1	xx (xx.x)	xx (xx.x)	xx (xx.x)	xx (xx.x)	xx (xx.x)
		2	xx (xx.x)	xx (xx.x)	xx (xx.x)	xx (xx.x)	xx (xx.x)
		3	xx (xx.x)	xx (xx.x)	xx (xx.x)	xx (xx.x)	xx (xx.x)
		4	xx (xx.x)	xx (xx.x)	xx (xx.x)	xx (xx.x)	xx (xx.x)

Note: NCI = National Cancer Institute, CTCAE = Common Terminology Criteria for Adverse Events.

Note: N is the number of subjects with both baseline and post-baseline assessments in a treatment group.

Note: Worst on-treatment result is defined as the worst result occurring after the administration of the first dose of doubleblind study medication.

Note: Baseline is defined as the last non-missing measurement taken prior to first dose of double-blind study medication.

Note: Grade refers to the severity. As a general guideline: Grade 1 is mild, Grade 2 is moderate, Grade 3 is severe or medically significant but not immediately life-threatening, and Grade 4 is life-threatening consequences.

Note: Percentages are calculated as (n/N)\*100.

Note: Grades are assigned using CTCAE Version x.xx.

Noven\HP-3070\XWA17541\Biostatistics\Production\Tables\xxxxx.sas ddmmmyyyy hh:mm

Programming note: Repeat for all tests planned in the protocol. For tests with grades in both high and low directions, show each direction separately, with high or low indicated in the laboratory test column.

Author: [name]

 Version Number:
 Draft 2

 Version Date:
 09Jan2017

 Page 88 of 144

Noven Pharmaceuticals, Inc. Protocol HP-3070-GL-04 Page 1 of x

Table 14.3.2.9 Clinical Laboratory I	Neutrophil Results Be	elow 1000 per Cubic I	Millimeter by Visit
	Safety Analysis Se	et	

Visit	Statistic	HP-3070 18.0 mg (N=xxx)	HP-3070 9.0 mg (N=xxx)	Placebo (N=xxx)
Baseline	N	xx	xx	xx
	n (%)	xx (xx.x)	xx (xx.x)	xx (xx.x)
Week 3	N	xx	xx	xx
	n (%)	xx (xx.x)	xx (xx.x)	xx (xx.x)
Week 6	N	xx	xx	xx
	n (%)	xx (xx.x)	xx (xx.x)	xx (xx.x)

Note: Baseline is defined as the last non-missing measurement taken prior to first dose of double-blind study medication.

Note: Percentages are calculated as (n/N)\*100, where N is the number of subjects with data at the given visit for each treatment group.

Note: Unscheduled visits are not included in this summary.

Noven/HP-3070/XWA17541/Biostatistics/Production/Tables/xxxxx.sas ddmmmyyyy hh:mm

Author:

[name]

Version Number: Version Date: Draft 2 09Jan2017 Page **89** of **144** 

Noven Pharmaceuticals, Inc. Protocol HP-3070-GL-04 Page 1 of x

#### Table 14.3.2.10 Clinical Laboratory Liver Function Abnormalities Safety Analysis Set

	HP-3070 18.0 mg	HP-3070 9.0 mg	Placebo
	(N=XXX)	(N=xxx)	(N=XXX)
Abnormality	n (%)	n (%)	n (%)
ALT > 3xULN	xx (xx.x)	xx (xx.x)	xx (xx.x)
AST > 3xULN	xx (xx.x)	xx (xx.x)	xx (xx.x)
ALP < 2xULN	xx (xx.x)	xx (xx.x)	xx (xx.x)
Potential Hy's Law Cases	xx (xx.x)	xx (xx.x)	xx (xx.x)
ALP <= 2xULN	xx (xx.x)	xx (xx.x)	xx (xx.x)
ALT >= 3xULN	xx (xx.x)	xx (xx.x)	xx (xx.x)
AST >= 3xULN	xx (xx.x)	xx (xx.x)	xx (xx.x)
Other Tests			
Creatine Kinase >= 3xULN	xx (xx.x)	xx (xx.x)	xx (xx.x)
Prolactin >= 4xULN	xx (xx.x)	xx (xx.x)	xx (xx.x)
Total Bilirubin >= 2xULN	xx (xx.x)	xx (xx.x)	xx (xx.x)

Note: ALT = Alanine Transaminase, AST = Aspartate Transaminase, ALP = Alkaline Phosphatase, ULN = Upper Limit of Normal.

Note: Potential Hy's Law Cases are defined as subjects who at any point during the study meet the criteria of ALT or AST > 3xULN, ALP < 2xULN, and Total Bilirubin >= 2xULN.

Note: Percentages are calculated as (n/N) \* 100.

Note: Values for ALT >=3xULN and AST >=3xULN are only presented for subjects that meet the criteria of ALP<=2xULN.

Noven\HP-3070\XWA17541\Biostatistics\Production\Tables\xxxxx.sas ddmmmyyyy hh:mm

Author:

[name]

Version Number: Version Date: Draft 2 09Jan2017 Page 90 of 144 Noven Pharmaceuticals Version No. 1.0 Protocol No. HP-3070-GL-04 14 September 2018

Page 1 of x

Noven Pharmaceuticals, Inc. STATISTICAL ANALYSIS PLAN: PROTOCOL HP-3070-GL-04

Noven Pharmaceuticals, Inc. Protocol HP-3070-GL-04

			HP-3070 18.0 mg	HP-3070 9.0 mg	Placebo
Parameter (Unit)	Visit	Statistic	(N=XXX)	(N=xxx)	(N=XXX)
PR Interval (msec)					
	Baseline	n	XX	хх	XX
		Mean	XX.X	XX.X	XX.X
		SD	XX.XX	XX.XX	XX.XX
		Median	XX	хх	XX
		Min	XX	ХХ	XX
		Max	XX	хх	XX
	Week 1	n	XX	XX	XX
		Mean	XX.X	XX.X	XX.X
		SD	XX.XX	XX.XX	XX.XX
		Median	XX	ХХ	XX
		Min	XX	XX	XX
		Max	XX	XX	XX
	Change from Baseline to Week	n	XX	XX	XX
	1				
		Mean	XX.X	XX.X	XX.X
		SD	XX.XX	XX.XX	XX.XX
		Median	XX	хх	XX
		Min	XX	хх	XX
		Max	XX	XX	XX
		Median Min Max	xx xx xx	xx xx xx	xx xx xx

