Laboratory findings will be classified as Low, Normal, and High relative to the laboratory. Central laboratories will also provide a classification of Clinically Significant or Not Clinically Significant abnormalities. Hematology and serum chemistry laboratory findings will also be graded according to National Cancer Institute Common Terminology Criteria for Adverse Events (NCI CTCAE) criteria, version 4.03, as applicable.

The following descriptive summaries will be provided for hematology, serum chemistry, and urinalysis data by treatment group:

- Actual and change from baseline by visit for quantitative measurements
- Shift from baseline to the worst on-treatment result for each category of result for categorical measurements. Worst on-treatment result is defined as the worst result occurring after the administration of the first dose of double-blind study medication.
- Number and percentage of subjects with an absolute neutrophil count of <1000 per mm3 by visit
- Number and percentage of subjects who meet the definition of potential Hy's Law cases at any point during the study. Potential Hy's Law cases are determined based on the FDA Guidance for Industry on Drug Induced Liver Industry, July 2009.
  - $\circ~$  Alanine transaminase (ALT) or Aspartate transaminase (AST) >3x upper limit of normal (ULN) and
  - Alkaline phosphatase (ALP) <2x ULN and
  - O Increase in bilirubin ≥2x ULN

Hy's Law evaluation based on the above

- (ALP) ≤2x ULN [for subjects that meet the criteria of ALP≤2, present ALT or AST elevations with ≥3x ULN]
- o AST ≥3x ULN

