		Mean	xx.x	XX.X	xx.x
		SD	XX.XX	xx.xx	XX.XX
		Median	XX	xx	XX
		Min	XX	XX	XX
		Max	XX	XX	xx

Table 14.3.2.1 Clinical Laboratory Quantitative Results and Change from Baseline by Visit - Hematology Safety Analysis Set

Note: Baseline is defined as the last non-missing measurement taken prior to first dose of double-blind study medication. Note: Unscheduled visits are not included in this summary.

Noven\HP-3070\XWA17541\Biostatistics\Production\Tables\xxxxx.sas ddmmmyyyy hh:mm

Programming note: Repeat at week 6 and for all tests planned in the protocol

Author:

[name]

Version Number: Version Date:

Draft 2 09Jan2017 Page 83 of 144 Noven Pharmaceuticals Version No. 1.0 Protocol No. HP-3070-GL-04 14 September 2018

Noven Pharmaceuticals, Inc. STATISTICAL ANALYSIS PLAN: PROTOCOL HP-3070-GL-04

Table 14.3.2.2 Clinical Laboratory Quantitative Results and Change from Baseline by Visit – Serum ChemistrySafety Analysis SetThis table will be similar to 14.3.2.1.

Table 14.3.2.3 Clinical Laboratory Quantitative Results and Change from Baseline by Visit – Urinalysis Safety Analysis Set

This table will be similar to 14.3.2.1.

Author: Ama

[name]

Version Number: Version Date: Draft 2 09Jan2017 Page **84** of **144** 

IMS Health & Quintiles are now

Noven Pharmaceuticals, Inc. Protocol HP-3070-GL-04 Page 1 of x

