Note: N is the number of subjects with both baseline and post-baseline assessments in a treatment group.

Note: Maximim on-treatment result is defined as the maximum result occurring after the administration of the first dose of doubleblind study medication.

Note: Baseline is defined as the last non-missing measurement taken prior to first dose of double-blind study medication.

Note: Percentages are calculated as (n/N) \* 100.

Note: Low is less than the normal low range value, Normal is inclusive of the normal low and high range values, and High is greater than the normal high range value.

Noven\HP-3070\XWA17541\Biostatistics\Production\Tables\xxxxx.sas ddmmmyyyy hh:mm Programming note: Repeat for all tests planned in the protocol

Author:

[name]

Version Number: Version Date: Draft 2 09Jan2017 Page **86** of **144** 

Protocol No. HP-3070-GL-04 14 September 2018

Noven Pharmaceuticals, Inc. STATISTICAL ANALYSIS PLAN: PROTOCOL HP-3070-GL-04

 Table 14.3.2.5.2 Clinical Laboratory Shifts from Baseline to Minimum On-Treatment Result – Hematology

 Safety Analysis Set

This table will be similar to 14.3.2.5.1.

Table 14.3.2.6.1 Clinical Laboratory Shifts from Baseline to Maximum On-Treatment Result – Serum Chemistry Safety Analysis Set This table will be similar to 14.3.2.5.1.

Table 14.3.2.6.2 Clinical Laboratory Shifts from Baseline to Minimum On-Treatment Result – Serum ChemistrySafety Analysis SetThis table will be similar to 14.3.2.5.1.

 Table 14.3.2.7.1 Clinical Laboratory Shifts from Baseline to Maximum On-Treatment Result – Urinalysis

 Safety Analysis Set

 This table will be similar to 14.3.2.5.1.

Table 14.3.2.7.2 Clinical Laboratory Shifts from Baseline to Minimum On-Treatment Result – UrinalysisSafety Analysis SetThis table will be similar to 14.3.2.5.1.

Author:

[name]

Version Number: Version Date:

Draft 2 09Jan2017 Page **87** of **144** 

Noven Pharmaceuticals, Inc. Protocol HP-3070-GL-04 Page 1 of x

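### Liver table 14.3.2.10 lists non-elevated ALP as an abnormality, has no row for raised ALP, and does not tie the ALP condition to the sample with the ALT/AST elevation

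*SAP*

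**What the plan says.** SAP 16.3 (Laboratory Evaluations) asks for the "Number and percentage of subjects who meet the definition of potential Hy's Law cases at any point during the study". The list below it joins ALT or AST above 3xULN, an ALP criterion ("Alkaline phosphatase (ALP) <2x ULN and") and bilirubin at 2xULN or more. A second block in the same section switches to inclusive cut-offs and uses ALP as a filter: "for subjects that meet the criteria of ALP≤2, present ALT or AST elevations with ≥3x ULN".

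Shell Table 14.3.2.10 carries this into a table whose row column is headed Abnormality, with n (%) per arm. The first block has ALT > 3xULN, AST > 3xULN, ALP < 2xULN and potential Hy's Law cases. The second has ALP <= 2xULN, ALT >= 3xULN and AST >= 3xULN. Creatine kinase, prolactin and total bilirubin follow. One footnote sets the condition for a potential Hy's Law case: "at any point during the study meet the criteria of ALT or AST > 3xULN, ALP < 2xULN, and Total Bilirubin >= 2xULN". Another limits the second block: "Values for ALT >=3xULN and AST >=3xULN are only presented for subjects that meet the criteria of ALP<=2xULN".

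Neither place says whether the ALP value is any value, the worst value, or the value from the sample with the ALT or AST elevation. Elsewhere in 16.3 such rules are given: the shift summaries define the worst on-treatment result, and the neutrophil count is reported by visit.

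**The concern.** Every other threshold row in the table counts an elevation. The ALP criterion runs the other way and is met by a normal value. That has two effects.

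First, an ALP row in an abnormality column counts the subjects without the abnormality, whichever ALP value is used.

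Second, a condition that a normal value satisfies is very weak unless it is fixed in time. The ALP condition is there to separate ALT/AST elevations without a raised ALP from those with one. If one normal ALP on another date is enough, it hardly does so. Potential Hy's Law counts are expected to be small, so one subject classified differently by two programmers, each following the text, would be visible in the safety report.

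**Working it through.** The plan states no figure on this point, so there is none to reproduce. The check is of table logic, with an illustrative count.

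**Inputs.** The laboratory shell for Table 14.3.2.1, which the serum chemistry table follows, shows Baseline and Week 3 with the programming note "Repeat at week 6 and for all tests planned in the protocol". That gives up to three scheduled ALP values per subject. N = 204 is the planned number of evaluable subjects per arm (SAP 3.1), used only as a denominator. The share q with ALP above 2xULN is not in the documents and is assumed to be 0.5% to 5%.

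**What the ALP rows count.**
- One value is enough, and elevations persist through all visits: N(1 − q) = 204 × 0.995 = 203.0, down to 204 × 0.95 = 193.8.
- One value is enough, and three values are independent: N(1 − q³) = 204 × (1 − 0.05³) = 203.97 even at q = 5%.
- The worst value decides: again N(1 − q), or 193.8 to 203.0, when q is the share of subjects. If q is instead a share per sample and the three samples are independent, N(1 − q)³ = 204 × 0.995³ = 201.0, down to 204 × 0.95³ = 174.9.

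On every reading the rows count subjects with non-elevated ALP. A row for any raised ALP would hold Nq = 1.0 to 10.2 subjects if elevations persist, or N(1 − (1 − q)³) = 3.0 to 29.1 if values are independent.

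**How many subjects the condition excludes when any value counts.** Nq = 1.0 to 10.2 of 204 if elevations persist at every visit. If values are independent, Nq³ = 204 × 0.05³ = 0.03 at most. Subjects with no ALP value come on top.

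**Constructed subjects** (multiples of ULN; ALT and bilirubin are the Week 3 values):

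| ALP at Baseline / Week 3 / Week 6 | ALT | Bilirubin | ALT >= 3x row, any ALP value | ALT >= 3x row, same sample | Hy's Law, each criterion at any time | Hy's Law, same sample |
|---|---|---|---|---|---|---|
| 0.8 / 4 / 1 | 5 | 1 | counted | not counted | not counted | not counted |
| 3 / 3 / 3 | 5 | 1 | not counted | not counted | not counted | not counted |
| 0.8 / 4 / 1 | 5 | 2.5 | counted | not counted | counted | not counted |
| 0.8 / 1 / 1 | 5 | 2.5 | counted | counted | counted | counted |

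The first and third subjects show the gap: ALP is raised in the sample that carries the ALT elevation, yet a normal ALP on another date lets them through. The second shows that the condition can still exclude someone.

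**The case against.** The strongest reply is that the any-time reading is supplied by the reader. The footnote on the restricted rows and the filter in 16.3 do not say which ALP value counts, and a worst-value or same-sample rule would make the filter work. In the Hy's Law definition, the any-point wording can also mean that all criteria are met at one time. This stands. The weak filter and the admission of a subject with concurrent raised ALP follow from one permitted reading. What the text establishes is that the timing is undefined.

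A reader might go further and infer that the ALP restriction excludes nobody. The documents do not support that: a subject with every ALP above the limit, or with none recorded, is excluded on any reading.

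A reader might also infer that a raised ALP goes unreported. It does not. Serum chemistry results are summarised by visit (Table 14.3.2.2). There is a table of "Clinical Laboratory Shifts from Baseline to Maximum On-Treatment Result – Serum Chemistry" (14.3.2.6.1), a CTCAE grade shift table where grades apply (14.3.2.8), and full listings. Those shift tables show Low/Normal/High or grade, not the 2xULN cut-off, and do not link ALP to a concurrent ALT or AST elevation.

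Nor would Hy's Law cases be missed. The row is labelled potential, and loose timing adds subjects rather than losing them. Potential Hy's Law events are also entered as adverse events of special interest and listed by subject.

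Finally, the ALP <= 2xULN row can fairly be read as the denominator of the two rows below it. It should be relabelled rather than deleted.

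**Conclusion.** The point holds in two parts of different strength.

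- **Certain on any reading.** Two rows present non-elevated ALP as an abnormality, and no row of this table counts a raised ALP. If 0.5% to 5% of subjects have ALP above 2xULN, each row holds about 194 to 204 of 204 per arm. That range is an assumption, and 204 is the planned evaluable number, not the size of the Safety Analysis Set.
- **Conditional.** The ALP condition is not tied to the sample with the ALT/AST elevation. On the any-time reading it excludes almost nobody: at most about 10 of 204, and only if 5% of subjects are raised at every visit. It can also admit a subject whose ALP was raised in that same sample, to the restricted rows and to the potential Hy's Law row.

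The strict and inclusive cut-offs also differ between the two blocks: <2x against <=2x for ALP, and >3x against >=3x for ALT/AST. They need reconciling. The table is descriptive and no efficacy result is affected, but the change is cheap and should be made.

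**What to change.** In shell Table 14.3.2.10:
- Drop the ALP < 2xULN row as an abnormality.
- Relabel the ALP <= 2xULN row as the denominator of the restricted ALT/AST rows, and say so in a footnote.
- Add a row for raised ALP (any value) whose cut-off is the exact complement of the one chosen for the restriction, so that no value falls on both sides.

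In SAP 16.3 and the footnotes:
- State that ALP is taken from the same sample as the ALT/AST elevation, both for the restricted rows and for potential Hy's Law cases. Where ALP is missing from that sample, use the nearest sample and flag it.
- Use one ALP cut-off and one ALT/AST cut-off throughout, or explain why the two blocks differ.

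The unrestricted ALT and AST rows stay, so no transaminase signal is hidden. Only ALP is tied to the sample, so a later bilirubin rise can still qualify. The cost is an edit to the SAP and one shell, and a merge by sample date in one program. The small downside is the flagged nearest-sample rule where ALP is missing.

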#### Table 14.3.3.1 12-Lead ECG Quantitative Results and Change from Baseline by Visit Safety Analysis Set

Note: ECG = Electrocardiogram.

Note: Baseline is defined as the last non-missing measurement taken prior to first dose of double-blind study medication. Note: Unscheduled visits are not included in this summary.

Noven\HP-3070\XWA17541\Biostatistics\Production\Tables\xxxxx.sas ddmmmyyyy hh:mm Programming note: Repeat for all visits and all tests planned in the protocol.

Author: Amanda S

[name]

Version Number: Version Date: Draft 2 09Jan2017 Page **91** of **144** 

Page 1 of x

#### Noven Pharmaceuticals, Inc. STATISTICAL ANALYSIS PLAN: PROTOCOL HP-3070-GL-04

Noven Pharmaceuticals, Inc. Protocol HP-3070-GL-04

Visit/		HP-3070 18.0 mg	HP-3070 9.0 mg	Placebo
Assessment	Statistic	(N=xxx)	(N=XXX)	(N=xxx)
Baseline	N	xx	xx	XX
Normal	n (%)	xx (xx.x)	xx (xx.x)	xx (xx.x)
Abnormal, Not Clinically Significant	n (%)	xx (xx.x)	xx (xx.x)	xx (xx.x)
Abnormal, Clinically Significant	n (%)	xx (xx.x)	xx (xx.x)	xx (xx.x)
Week 1	N	xx	xx	XX
Normal	n (%)	xx (xx.x)	xx (xx.x)	xx (xx.x)
Abnormal, Not Clinically Significant	n (%)	xx (xx.x)	xx (xx.x)	xx (xx.x)
Abnormal, Clinically Significant	n (%)	xx (xx.x)	xx (xx.x)	xx (xx.x)
Week 2	N	XX	XX	XX
Normal	n (%)	xx (xx.x)	xx (xx.x)	xx (xx.x)
Abnormal, Not Clinically Significant	n (%)	xx (xx.x)	xx (xx.x)	xx (xx.x)
Abnormal, Clinically Significant	n (%)	xx (xx.x)	xx (xx.x)	xx (xx.x)

Table 14.3.3.2 12-Lead ECG Overall Assessment by Visit Safety Analysis Set

Note: ECG = Electrocardiogram.

Note: Overall assessment of ECG is based on investigator's judgment.

Note: Baseline is defined as the last non-missing measurement taken prior to first dose of double-blind study medication.

Note: Unscheduled visits are not included in this summary.

Note: Percentages are calculated as (n/N) \* 100, where N is the number of subjects with data at the given visit.

Noven\HP-3070\XWA17541\Biostatistics\Production\Tables\xxxxx.sas ddmmmyyyy hh:mm Programming note: Repeat for all visits.

Author:

[name]

Version Number:

Version Date:

Draft 2 09Jan2017 Page **92** of **144**

Noven Pharmaceuticals, Inc. Protocol HP-3070-GL-04 Page 1 of x

Table 14.3.3.3 12-Lead ECG Overall Assessment Shifts from Baseline to Worst On-Treatment Res	ult
Safety Analysis Set	

		Worst On-Treatment Result			
		Normal	Abnormal, NCS	Abnormal, CS	
Treatment Group	Baseline Result	n (%)	n (%)	n (%)	
HP-3070 18.0 mg (N=XX)	Normal	xx (xx.x)	xx (xx.x)	xx (xx.x)	
	Abnormal, NCS	xx (xx.x)	xx (xx.x)	xx (xx.x)	
	Abnormal, CS	xx (xx.x)	xx (xx.x)	xx (xx.x)	
HP-3070 9.0 mg (N=XX)	Normal	xx (xx.x)	xx (xx.x)	xx (xx.x)	
	Abnormal, NCS	xx (xx.x)	xx (xx.x)	xx (xx.x)	
	Abnormal, CS	xx (xx.x)	xx (xx.x)	xx (xx.x)	
Placebo (N=XX)	Normal	xx (xx.x)	xx (xx.x)	xx (xx.x)	
	Abnormal, NCS	xx (xx.x)	xx (xx.x)	xx (xx.x)	
	Abnormal, CS	xx (xx.x)	xx (xx.x)	xx (xx.x)	

Note: ECG = Electrocardiogram, NCS = Not Clinically Significant, CS = Clinically Significant

Note: N is the number of subjects with both baseline and post-baseline assessments in a treatment group.

Note: Worst on-treatment result is defined as the worst result occurring after the administration of the first dose of doubleblind study medication.

Note: Baseline is defined as the last non-missing measurement taken prior to first dose of double-blind study medication. Note: Percentages are calculated as (n/N) \* 100.

Noven/HP-3070/XWA17541/Biostatistics/Production/Tables/xxxxx.sas ddmmmyyyy hh:mm

Author:

[name]

Version Number:

Version Date:

Draft 2 09Jan2017 Page **93** of **144** 

Page 1 of x

### Noven Pharmaceuticals, Inc. STATISTICAL ANALYSIS PLAN: PROTOCOL HP-3070-GL-04

Noven Pharmaceuticals, Inc. Protocol HP-3070-GL-04

# Table 14.3.3.4 12-Lead ECG Markedly Abnormal Results by Visit Safety Analysis Set

Visit/		HP-3070 18.0 mg	HP-3070 9.0 mg	Placebo
Abnormality	Statistic	(N=XXX)	(N=XXX)	(N=xxx)
Overall Post-baseline	N	XX	xx	XX
Any Marked Abnormality	n (%)	xx (xx.x)	xx (xx.x)	xx (xx.x)
OT Interval				
Result > 450 msec	n (%)	xx (xx.x)	xx (xx.x)	xx (xx.x)
Result > 480 msec	n (%)	xx (xx.x)	xx (xx.x)	xx (xx.x)
Result > 500 msec	n (%)	xx (xx.x)	xx (xx.x)	xx (xx.x)
Change from Baseline >= 30 msec	n (%)	xx (xx.x)	xx (xx.x)	xx (xx.x)
Change from Baseline >= 60 msec	n (%)	xx (xx.x)	xx (xx.x)	xx (xx.x)
QTcB Interval				
Result > 450 msec	n (%)	xx (xx.x)	xx (xx.x)	xx (xx.x)
Result > 480 msec	n (%)	xx (xx.x)	xx (xx.x)	xx (xx.x)
Result > 500 msec	n (%)	xx (xx.x)	xx (xx.x)	xx (xx.x)
CFB >= 30 msec	n (%)	xx (xx.x)	xx (xx.x)	xx (xx.x)
CFB >= 60 msec	n (%)	xx (xx.x)	xx (xx.x)	xx (xx.x)

Note: ECG = Electrocardiogram, QTcB = QT interval corrected by Bazett's formula, QTcF = QT interval corrected by Fridericia's formula, HR = Heart Rate.

Note: Baseline is defined as the last non-missing measurement taken prior to first dose of double-blind study medication.

Note: Percentages are calculated as (n/N) \* 100, where N is the number of subjects with data at the given visit.

Note: Unscheduled visits are not included in this summary.

Noven\HP-3070\XWA17541\Biostatistics\Production\Tables\xxxxx.sas ddmmmyyyy hh:mm

Author:

[name]

Version Number: Version Date: Draft 2 09Jan2017 Page **94** of **144** 

Page 2 of x

Noven Pharmaceuticals, Inc. STATISTICAL ANALYSIS PLAN: PROTOCOL HP-3070-GL-04

Noven Pharmaceuticals, Inc. Protocol HP-3070-GL-04

Visit/		HP-3070 18.0 mg	HP-3070 9.0 mg	Placebo
Abnormality	Statistic	(N=XXX)	(N=XXX)	(N=XXX)
QTcF Interval				
Result > 450 msec	n (%)	xx (xx.x)	xx (xx.x)	xx (xx.x)
Result > 480 msec	n (%)	xx (xx.x)	xx (xx.x)	xx (xx.x)
Result > 500 msec	n (%)	xx (xx.x)	xx (xx.x)	xx (xx.x)
Change from Baseline >= 30 msec	n (%)	xx (xx.x)	xx (xx.x)	xx (xx.x)
Change from Baseline >= 60 msec	n (%)	xx (xx.x)	xx (xx.x)	xx (xx.x)
HR				
>= 100 bpm	n (%)	xx (xx.x)	xx (xx.x)	xx (xx.x)
PR Interval				
>= 210 msec	n (%)	xx (xx.x)	xx (xx.x)	xx (xx.x)
QRS Interval				
>= 120 msec	n (%)	xx (xx.x)	xx (xx.x)	xx (xx.x)
Week 1				

Table 14.3.3.4 12-Lead ECG Markedly Abnormal Results by Visit Safety Analysis Set

#### ...

Note: ECG = Electrocardiogram, QTcB = QT interval corrected by Bazett's formula, QTcF = QT interval corrected by Fridericia's formula, HR = Heart Rate,

Note: Baseline is defined as the last non-missing measurement taken prior to first dose of double-blind study medication. Note: Percentages are calculated as (n/N) \*100, where N is the number of subjects with data at the given visit. Note: Unscheduled visits are not included in this summary.

Noven\HP-3070\XWA17541\Biostatistics\Production\Tables\xxxxx.sas ddmmmyyyy hh:mm Programming note: Repeat for week 2 through 6.

Author: [name]

Version Number:

Version Date:

Draft 2 09Jan2017 Page **95** of **144** 

Noven Pharmaceuticals, Inc. Protocol HP-3070-GL-04 Page 1 of x

